## 9.5 Data Analyses

Data analysis will be conducted in two phases: after baseline data retrieval; and after all study data have been retrieved.

**After baseline data retrieval**, data analysis will be conducted to compare and assess the equivalence of baseline cognitive impairment, medications, and demographic characteristics across the intervention group and control group. Statistical analyses of baseline characteristics between participants for primary and secondary outcomes are the following: The Shapiro-Wilk test will be used to confirm that the random sample is normally distributed for the outcome variables studied. Student t-test will be used to confirm that mean variables are not significantly different between intervention and control groups (e.g., percentage with moderate versus mild cognitive impairment). Chi-square test will be used to confirm that dichotomous variables (e.g., sex) are not significantly different between intervention and control groups. Wilcoxon rank-sum will be used to confirm that ordinal variables (e.g., cognitive screening score) are not significantly different between groups.

Three outcome measures in this pragmatic study are used to assess cognition: MoCA, MMSE and SLUMS. 2-points change in the MoCA, MMSE or SLUMS will be used to indicate clinically meaningful cognitive change (either improvement or decline). Additionally, the number of points change on the cognitive screening instruments that are indicative of meaningful change will be evaluated using a distribution-based approach based on baseline cognitive assessment data from the three sites to inform the selection of instruments and threshold cut-offs for clinically meaningful change for a full-scale trial.

**After all study data have been retrieved**, including baseline and follow-up data from intervention and control groups, MoCA, SLUMS, and MMSE data elements will be examined for their completeness/missingness, and findings of missing data will be reported to the respective HCS. In addition to evaluating the completeness/missingness of data (i.e., the percentage of complete (non-missing) data elements), we also will determine the frequency of use of the three instruments (i.e., the percentage of study participants who were assessed with each instrument). If the outcomes could not be retrieved for some individuals, we will use multiple imputation with chains equations to address the missingness.

We will follow an intention-to-treat protocol whereby all patients who are randomized are included in statistical analyses according to the group (intervention or control) to which they were assigned, regardless of whether they participate in V-CST (McCoy, 2017). We will determine the distribution of each measure's change in scores and will apply the Cohen criteria whereby the values of the standardized response mean and effect size (i.e., the change in mean scores divided by the standard deviation (SD) of the baseline scores) are used as the indices of responsiveness. For the MoCA, Wu and colleagues (2019)

used the Cohen criteria and classified these effect sizes as large ( $>0.8$ ), moderate ( $0.5-0.8$ ), and small ( $<0.5$ ), adopting a threshold value of 0.5 SD.

When different cognitive assessments are used pre- and post-intervention, a change from using the MoCA or the SLUMS to using the MMSE will initially indicate a clinically meaningful *reduction* in cognitive function, and a change from using the MMSE to the MoCA or SLUMS will initially indicate a clinically meaningful *improvement* in cognitive function. Any such *reductions* or *improvements* in cognitive function determined based on change in instrument use will be compared against the actual assessment scores using the literature for reference. For example, a shift from getting a score of 16 using the MoCA to a score of 16 using the MMSE would be verified as a clinically meaningful change from mild to moderate dementia (Saczynski et al 2015, Table 1). To validate any such initial indications of reductions or improvements in cognitive function that are determined based on a change in instrument used, verification of the change in cognitive function will be requested from the referring physician.

Table 1. Cut scores for MoCA and MMSE (Saczynski et al 2015)

MoCA	Cognition Level	MMSE
<math>\leq 30</math>	Normal	<math>\leq 30</math>
<math>\leq 23</math>	MCI	<math>\leq 27</math>
<math>\leq 17</math>	Mild Dementia	<math>\leq 23</math>
<math>\leq 9</math>	Moderate Dementia	<math>\leq 17</math>

For those using the same instrument in both baseline and follow-up, we also will assess the frequency whether there is a clinically meaningful reduction in cognitive function.

The estimand of the primary outcome would be the marginal difference in proportions of individuals that see clinically meaningful reduction in cognitive function.

Data analysis to test the study hypotheses is described below.

Testing of H1 will entail comparing the proportions of clinically meaningful reduction in cognitive function between the intervention group and the control group. Factors that affect the primary outcome will be controlled for by logistic regression analyses, which include the number of health comorbidities, baseline cognitive function, number of psychotropic medications, diagnoses and sites. With the study sample size, assuming that the rate of reduction in cognitive function is 50% we would be able to detect a 22% decrease in the rate of cognitive decline with 80% power and nominal level of 5%.

Testing of H2 will entail comparing the proportions of clinically meaningful improvement in cognitive function between the intervention group and the control group. Factors that affect the primary outcome will be controlled for by logistic regression analyses, which include the number of health comorbidities, baseline cognitive function, number of psychotropic medications, diagnoses and sites.

Testing of H3 and H4 will entail comparing the marginal prevalence of new prescriptions for or increased dosages of psychotropic medications between the intervention group and the control group. Logistic regression would be used to adjust for baseline clinical and demographic characteristics as in H1.

Testing of H5 will entail calculating the marginal percentage of intervention group participants who accepted the referral, the percentage that accepted the referral who enroll in V-CST, the percentage of V-CST sessions attended by enrolled participants, and the percentage of enrolled participants who ceased

attending V-CST between S1 and the last session S14. To adjust for baseline clinical and demographic variables we will use logistic regression.

Because some patients who are randomized to the intervention group may not assent to the V-CST referral, we also will conduct a secondary principal stratification analysis (Frangakis & Rubin, 2022). This analysis would be used to estimate the effect of the intervention among patients who complied with the treatment (i.e., participants assigned to the intervention group who enroll in V-CST) by performing principal stratification analysis to adjust for those participants assigned to the intervention group who did not enroll in V-CST. We will follow the analysis used in Mealli & Imbens (2004) and Hirano et al (2000).

In addition to hypothesis testing, data collected by the V-CST facilitators, including the Geriatric Depression Scale (GDS), Engagement and Independence in Dementia Questionnaire (EID-Q) – Subscales 3-5, and Positive Psychology Outcome Measure (PPOM), will be examined to detect any changes in scores from before to after treatment.

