### 9.4.1 Primary Outcome

The primary outcome to be assessed is clinically meaningful reduction in cognitive impairment. Reduction in cognitive impairment from baseline to post-intervention will be determined by comparing pre- and post-scores on standardized measures of cognition (i.e., the MOCA, SLUMS, or MMSE). A change—either increase or decrease—of 2 points or greater will indicate a clinically meaningful change. Primary outcome data will be retrieved from participating site records.

The MOCA, SLUMS, and MMSE are standardized screening tools commonly used by clinicians to determine a person's cognitive status. Although each of these instruments is relatively quick and easy to use and calculated to a total score of up to 30, each also has different sensitivity to mild cognitive impairment and length of time for completion, and clinicians use a combination of the different instruments to assess cognition rather than any one instrument exclusively. Based on prior literature, a decrease of about 1 point on each instrument is anticipated in the control group over the study period.

**MMSE** is a widely used, 12-item assessment of cognitive function that evaluates orientation to time and place, language, registration and recall of words, attention and calculation, and visual construction, and takes about 10 minutes to complete (Howland et al., 2016). MMSE assesses several areas, including orientation, immediate memory, short-term memory, and language functioning, each of which is scored independently for a total of 30 points (Slavych, 2019). MMSE has significant ceiling effects, reliably detecting dementia but not MCI (Howland et al., 2016). MMSE's brevity and ease of administration are strengths, whereas MMSE's disadvantages include its inability to detect subtle memory losses (Slavych, 2019). In a Cochrane review of CST, 10 studies involving 600 participants used the MMSE, finding the overall mean difference was 1.74 points (95% CI 1.13 to 2.36) and statistically significant ( $Z = 5.57$ ,  $P < 0.00001$ ) (Woods et al., 2012). In studies of people with stroke/transient ischemic attack, cerebrovascular disease, Tan et al (2017) and Kalmijn et al (1996) defined cognitive decline as a reduction of  $\geq 2$  points in the MMSE over two consecutive screenings from 3–6 months to 1 year.

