### **10.2 Data Management**

Data from the HCSs will be gathered through a targeted raw data pull that includes only select information about study participants from the EHRs. First, clinical sites will retrieve patient data from their records based on the study inclusion/exclusion criteria, including demographic information, medications, diagnoses, and cognitive function (MoCA, SLUMS, and/or MMSE).

The research sites Yale and UConn will share data directly with UMass via Sharepoint, and will include data on V-CST enrollment, attendance, attrition, fidelity to the treatment administration manual, adverse events, and three measures standardly collected before and after participation in V-CST, the Geriatric Depression Scale, Engagement and Independence in Dementia Questionnaire - Subscales 3-5, and the Positive Psychology Outcome Measure. CaringKind will provide patient data to the referring HCS physician per standard of care. Once data is securely transferred to UMass, all study data will be stored in Microsoft Teams which is a HIPAA compliant password protected server only accessible to the UMass research team.

Confidentiality of participant records will be maintained by HCSs uploading all data to a secured server in a Sharepoint file. Access to the Sharepoint file will be limited to the PI and study coordinator at UMass, who will clean and deidentify data and assigning a unique study identifier for each participant. The UMass team will maintain a de-identified and PHI enrollment internally for communication between the research sites to ensure HIPAA compliance and protection against loss of confidentiality. UMass will be the primary location for all data management, maintenance, and distribution. All data will then be transferred from Sharepoint into MS teams to be maintained and clean accessible to only the UMass team. Sharepoint will only be used to transfer data and will not be the primary storage platform. MS teams is a HIPAA compliant and password protected platform maintained and stored on a UMass IT server. The de-

identified data will be transferred it to the study biostatistician at Brown University in an encrypted email. Using the deidentified data provided by UMass, [name], study biostatistician, will conduct data analysis, interpret results, and report findings to the PI also through encrypted email messaging.

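### Baseline adjustment and the 2-point responder rule take no account of which, or how many, of the three cognitive instruments a patient had

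*Combined protocol and SAP*

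**What the plan says.** Section 4.1 admits patients on a MoCA of 10-26, a SLUMS of 10-26 or an MMSE of 13-24. Section 9.4.1 notes that the instruments differ in sensitivity and that "clinicians use a combination of the different instruments to assess cognition rather than any one instrument exclusively". The data pull in Section 10.2 asks for "cognitive function (MoCA, SLUMS, and/or MMSE".

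The responder rule in Section 9.5 is that "2-points change in the MoCA, MMSE or SLUMS will be used to indicate clinically meaningful cognitive change (either improvement or decline". Decline is the event for H1 and improvement the event for H2. If the instrument differs between the two visits, the direction of the switch gives a first classification. That is then checked against the scores and with the physician, as in the example of "a shift from getting a score of 16 using the MoCA to a score of 16 using the MMSE".

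The logistic models for H1 and H2 include "baseline cognitive function, number of psychotropic medications, diagnoses and sites", together with the number of comorbidities. The baseline comparison names the cognitive screening score as an ordinal variable for a rank-sum test. Neither place says which instrument's score enters, how scores are made comparable, or whether instrument is a covariate. No passage selects one instrument when a patient has two, or says how opposite changes are resolved.

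**The concern.** There are two separate gaps.

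The first is the baseline covariate. Table 1 gives the same number a different meaning on the MoCA and the MMSE. If scores enter as recorded, the covariate orders some patients wrongly and explains less of the outcome than the same data could. A chance imbalance in instrument mix between arms would also go uncorrected. The rank-sum comparison has the same weakness.

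The second is the counting rule. With two same-instrument pairs, a patient has two chances to meet the decline definition and can meet the improvement definition as well. The event rate then depends on how many tests were given. The trial is not blinded (Section 4.3), follow-up testing is part of usual care, and the referring physician carries out the post-V-CST data screening (Section 6.2.4). The number of tests could therefore differ by arm for reasons unrelated to cognition.

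**Working it through.** **1. The plan's own figure.** Section 9.5 assumes a 50% rate of decline and claims 80% power for a 22% decrease at the 5% level. Section 9.2 gives 56 and 112 participants. Reading 22% as percentage points (28% v 50%), two-sided:

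- pooled rate = (56 × 0.28 + 112 × 0.50)/168 = 0.4267
- SE under the null = √[0.4267 × 0.5733 × (1/56 + 1/112)] = 0.0809
- SE under the alternative = √[0.28 × 0.72/56 + 0.50 × 0.50/112] = 0.0764
- power = Φ[(0.22 − 1.96 × 0.0809)/0.0764] = Φ(0.80) = 78.9%

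The statement reproduces and is not in dispute. The 50% rate is, however, not tied to any rule for patients with two instruments.

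**2. Severity by Table 1.** Each integer score was classified by the cut scores:

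| Score | MoCA | MMSE |
|---|---|---|
| 10-17 | mild dementia | moderate dementia |
| 18-23 | MCI | mild dementia |
| 24-26 | normal | MCI |

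All 17 scores from 10 to 26 differ by one level, including all 12 (13-24) that are eligible on both instruments. Raw order can even reverse severity: a MoCA of 18 (MCI) lies 5 points below an MMSE of 23 (mild dementia). Table 1 has no SLUMS column.

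**3. One pair against two.** Inputs: mean change -1 on each instrument (Section 9.4.1, control group). SD of change 2-3 and between-instrument correlation 0.3-0.7 are assumptions, because the documents give neither. Changes are bivariate normal, rounded to whole points, so decline means below -1.5 and improvement above +1.5.

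- One pair: P(decline) = Φ[(-1.5 + 1)/SD] = Φ(-0.25) = 40.1% at SD 2, and Φ(-0.167) = 43.4% at SD 3.
- Two pairs: P(decline on either) = 2 × P(one) − P(both), by simulation of 400,000 patients per row.

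| SD | Correlation | Decline, one pair | Decline, either of two | Decline on one and improvement on the other |
|---|---|---|---|---|
| 2 | 0.3 | 40.1% | 59.6% | 4.5% |
| 2 | 0.5 | 40.1% | 56.3% | 2.2% |
| 2 | 0.7 | 40.1% | 52.4% | 0.6% |
| 3 | 0.3 | 43.4% | 63.2% | 11.0% |
| 3 | 0.5 | 43.4% | 59.9% | 6.8% |
| 3 | 0.7 | 43.4% | 55.9% | 2.8% |

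Check by hand at SD 2 and correlation 0: 1 − (1 − 0.401)² = 64.1%, which agrees with the simulation. Widening to SD 2-4 and correlation 0-0.7 takes the last column to 0.6-24%. A concrete case is MoCA 18 to 16 with MMSE 20 to 22, which meets both definitions.

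**4. Effect on the whole trial.** In patients with two pairs, the excess over one pair is 52.4 − 40.1 = 12.3 points up to 63.2 − 43.4 = 19.8 points. If a share f of patients has two pairs, the overall decline rate rises by f × (12.3 to 19.8) points. The documents do not give f:

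| f (assumed) | Rise in decline rate |
|---|---|
| 10% | 1.2-2.0 points |
| 20% | 2.5-4.0 points |
| 50% | 6.2-9.9 points |

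At f = 20%, 168 × 0.20 = 33.6 patients have two pairs. Between 33.6 × 0.006 = 0.2 and 33.6 × 0.11 = 3.7 of them would count under both hypotheses, or about 8 at the widest 24%. If f differed between arms by 20 percentage points, the spurious difference would be 2.5-4.0 points, against the 22 points that the trial is sized to detect.

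**The case against.** A reader might infer that the plan treats the three instruments as one 30-point scale. The documents do not support that. Section 9.4.1 says the instruments differ, Section 9.5 examines each measure's change separately, and a switch of instrument has its own rule with a crosswalk and physician verification. Outcome change is evidently taken within instrument.

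A reader might also infer from the unequal widths of the Table 1 bands that 2 points is not the same event on each instrument. That does not follow. The width of a diagnostic band does not measure within-person responsiveness, and Section 9.4.1 supports the 2-point cut separately for the MMSE and the MoCA.

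The remaining objections have some force:

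- Pooling of raw baseline scores is inferred from silence. The baseline comparison also mentions moderate versus mild impairment, and diagnoses and sites are in the models, which may absorb part of the difference.
- Under randomization an imprecise covariate mainly costs precision, not validity.
- The listing of three instruments may simply mean whichever one the patient had, and the remark on combinations may describe practice across a clinic. Nothing shows that patients have two instruments at both visits, or that testing differs by arm.
- Section 10.1 gives feasibility of outcome collection as the main purpose.

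These points limit the size of the problem. They do not supply the missing rule: two analysts could still code the same record differently for the primary outcome.

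**Conclusion.** The point holds in a limited form. The baseline covariate and the baseline comparison are not defined across instruments, although Table 1 places equal MoCA and MMSE scores one severity level apart throughout 10-26. The cost is mainly precision, and the documents do not allow it to be quantified.

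The responder rule, read literally, lets the chance of decline rise with the number of instruments and lets decline and improvement overlap. For patients with two pairs the size is as tabulated, and it rests on the assumed SD, correlation and normality. For the trial as a whole it depends on a share that is not reported and may be small. Arm-dependent testing is possible in an open-label trial, but it is not shown. The power statement stands as written. Because H1 is the primary hypothesis and the remedy uses data already being collected, the change should be made before outcome data are analyzed.

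**What to change.** 1. **Covariate.** Add baseline instrument to the H1 and H2 models and to the imputation model. Enter baseline cognition as a score standardized within instrument, with both arms combined. Both terms are needed, because standardizing removes level differences between instrument groups and the instrument term lets them back in. The Table 1 level is not a substitute, as it cannot be assigned to SLUMS patients. Run the baseline rank-sum comparison within instrument.
2. **One pair per participant.** Among instruments scored at both visits, choose one by an instrument priority order fixed in advance, working from the dated scores with the arm column removed. Use the existing switch rule only when no same-instrument pair exists. Otherwise a patient with a MoCA at both visits and an added MMSE at follow-up could be an improver on the MoCA and a decliner by switch.
3. **Outcome coding.** Code decline, stable and improved as mutually exclusive categories of that one pair. Overlap is then zero by construction.

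The cost is some SAP wording and up to two degrees of freedom for three instruments. Second-instrument scores move to a sensitivity analysis. The pair rule stops the number of tests from affecting the event rate, but it cannot remove a clinician's influence on which instrument was given. The instrument-frequency table already planned in Section 9.5 should therefore be shown by arm, with the number of patients who have two pairs.

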### **3 STUDY DESIGN**

The study design that will be piloted is a two-armed randomized pilot ePCT. This pilot trial aims to evaluate it is possible to use the study design to determine if cognitive decline is experienced less commonly among intervention group participants than control group members.

The study population will be persons with mild cognitive impairment and/or mild to moderate dementia, and subject participants will be randomly sampled from two institutions: UConn and Yale. Eligible participants will be identified from medical records, verified appropriate for V-CST by physician review, and randomized in a 1:2 ratio into the interventional or control arms. The intervention will be referral for V-CST and the control will receive no referral. Unequal randomization is used in this trial because randomizing more participants to the control arm allows greater overall participation.

A total of 168 eligible participants will be enrolled into the study, and enrollment will close once the intervention group has 56 participants and the control group has 112 participants. Analysis will examine baseline demographic, diagnosis, and medication variables between the intervention and control groups to ensure they are balanced. Any identified imbalances will be addressed using regression adjustments.

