### **6.2.1 Pre-Treatment Data Screening**

Pre-treatment data screening will be conducted first to determine which patients at each HCS are eligible for the study. These evaluations will be conducted by the HCSs examining their electronic health records to identify eligible participants based on the study's inclusion and exclusion criteria.

Eligible participants will be randomized at each site and allocated into either the control or intervention arms. At this time, the following data will be abstracted from HCS records on the eligible participants: ICD-10 code(s) for dementia; demographics; medications; and cognitive screening scores.

Participants randomized to the intervention arm will be referred for V-CST.

Pre-Treatment Data Screening will conclude with HCSs uploading the abstracted data to the project Sharepoint file.

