Raw data will be extracted from the research sites electronic medical record each participant's name, age, ICD-10 dementia diagnosis code(s), psychotropic medications and dosages, and cognitive test scores. These data will be stored in a HIPAA-compliant Sharepoint file. The referring sites will be granted access to upload their patient data, and access to patient data will be restricted to the PI and study coordinator. Sharepoint is an encrypted secure file transfer platform maintained by the UMass IT department, with access to Sharepoint granted and maintained by the UMass IT department. All data will then be transferred from Sharepoint into MS teams to be maintained and clean accessible to only the UMB team. Sharepoint will only be used to transfer data and will not be the primary storage platform. MS teams is a HIPAA compliant and password protected platform maintained and stored on a UMass IT server.

Data previous stored at UMB will be transferred via Sharepoint to UMass to be permanently stored/maintained by the UMass study team and PI. All UMB servers will be scrubbed of all data for this project and will not store any data.

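### Age is collected but absent from the H1/H2 covariate list; the only stated route into the primary model is a baseline imbalance check, and the H3/H4 reference to demographics in H1 has no referent

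*Combined protocol and SAP*

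**What the plan says.** In section 9.5 the logistic model for H1 controls for factors "which include the number of health comorbidities, baseline cognitive function, number of psychotropic medications, diagnoses and sites", and the H2 paragraph repeats the same five. For H3 and H4 the same section says: "Logistic regression would be used to adjust for baseline clinical and demographic characteristics as in H1". H5 is also to be adjusted for demographic variables.

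Age is available. Section 7.4 lists the extract as "name, age, ICD-10 dementia diagnosis code(s), psychotropic medications and dosages, and cognitive test scores", and section 6.2.1 has the sites abstract "ICD-10 code(s) for dementia; demographics; medications; and cognitive screening scores" for all eligible participants.

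Section 3 provides a fallback: "Analysis will examine baseline demographic, diagnosis, and medication variables between the intervention and control groups to ensure they are balanced", and then "Any identified imbalances will be addressed using regression adjustments". Section 9.5 gives the means of checking, for example "Student t-test will be used to confirm that mean variables are not significantly different between intervention and control groups", with chi-square and Wilcoxon tests for other variable types.

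The target quantity in section 9.5 is a risk difference: "The estimand of the primary outcome would be the marginal difference in proportions of individuals that see clinically meaningful reduction in cognitive function".

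**The concern.** There are two defects.

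First, the cross-reference fails. An analyst fitting H3 or H4 is sent to H1 for a set of demographic covariates and finds none. Either the H1 list lacks variables that were intended, or the H3/H4 wording is wrong.

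Second, the primary model is not fixed for age. Age enters if a baseline comparison flags it and otherwise, on the text, does not. The covariates of the primary analysis would then depend on a baseline result. A significance test is also a poor guide to which covariates matter: it responds to the size of the gap between arms and ignores how prognostic the variable is. In an open-label trial the primary covariate set should be settled in advance. At stake are the prespecification of the primary model, agreement between primary and secondary analyses, and possibly a little precision.

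**Working it through.** **1. The plan's own figure.** Inputs from section 9.5: 112 controls at 50%, 56 intervention patients 22 points lower (28%), 5% level. Sidedness is not stated; two-sided is assumed.

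- Pooled rate = (112×0.50 + 56×0.28)/168 = 0.4267
- SE under the null = √[0.4267×0.5733×(1/112+1/56)] = 0.0809
- SE under the alternative = √[0.25/112 + 0.2016/56] = 0.0764
- Power = Φ[(0.22 − 1.96×0.0809)/0.0764] = Φ(0.803) = 78.9%

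This agrees with the stated 80%; the detectable difference at 80% is 22.3 points. Reading the 22% as relative (50% vs 39%) gives 26.7% and does not reproduce. The plan's figure is therefore an absolute, unadjusted comparison.

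**2. What the baseline check could leave.** The chance difference in mean age between arms has SD √(1/56+1/112) = 0.164 age-SDs. If flagging rests on a two-sided 5% test (the level of the baseline tests is not stated), the threshold is 1.96×0.164 = 0.32 SD, and about 95% of randomisations would not flag age however prognostic it is. The chance of a gap above 0.2 SD is 22%.

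Shift in the **unadjusted** risk difference, with age standard normal, a 50% event rate and an assumed odds ratio (OR) per SD:

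| OR per SD | gap 0.2 SD | gap 0.32 SD |
|---|---|---|
| 1.1 | 0.5 points | 0.8 points |
| 1.3 | 1.3 | 2.1 |
| 1.5 | 2.0 | 3.1 |
| 2.0 | 3.1 | 5.0 |

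These are upper guides. The planned analysis is adjusted, and any age effect carried by cognition, diagnosis or comorbidity is partly removed already.

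**3. Precision from adding age.** The effect of age is not in the documents, so a range is assumed. Each simulation had 4,000 trials per case, 50% vs 28%, 112 vs 56, and a logistic model standardised to a risk difference.

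- A: baseline cognition in the model (OR 1.5 per SD), age independent of it.
- B: baseline cognition (log OR 0.5 per SD) and site in the model.
- C: all five listed covariates in the model, with assumed effects, and age correlated 0.4 with cognition, comorbidity and diagnosis.

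| OR per SD | A: variance ratio, with/without age | B: power without → with | C: power without → with | C: variance ratio |
|---|---|---|---|---|
| 1.0 | 1.01 | 83.4 → 82.8% | 83.9 → 83.6% | 1.005 |
| 1.3 | 1.00 | 83.0 → 83.9% | 86.0 → 86.4% | 0.998 |
| 1.5 (A), 1.6 (B, C) | 0.98 | 83.0 → 84.8% | 85.4 → 86.6% | 0.981 |
| 2.0 | 0.90 | 82.8 → 85.7% | 87.2 → 88.7% | 0.959 |

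The simulation error of one power figure is √(0.83×0.17/4000) = 0.6 points, so the small falls at OR 1.0 are of that order. Type I error in B at OR 2.0 was 5.6% without age and 5.8% with it.

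The simulated starting power exceeds 78.9% mainly because an unpooled standard error is used: Φ(0.22/0.0764 − 1.96) = 82.1%. Only the change within a row is informative.

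A cruder route scales both standard errors in step 1 by √(1−R²), R² being the share of outcome variance explained by age. R² of 0.01, 0.02, 0.05 and 0.10 gives power of 79.3%, 79.8%, 81.0% and 83.1%, and detectable differences of 22.2, 22.1, 21.7 and 21.2 points. An OR of 2.0 corresponds to R² of about 0.097. The top of this range is about 4 points of power. The simulations fit the model and estimand concerned and are preferred.

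**The case against.** **Section 3 already covers imbalance.** A reader might infer that a chance age imbalance will sit in the primary result. The documents do not support that: a flagged imbalance is to be adjusted for. Chance imbalance under randomisation is also part of the sampling error that the standard error describes; it does not bias the estimator. What remains is that adjustment is conditional and a smaller gap can pass.

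**The precision loss is not demonstrated.** A reader might infer that worthwhile power is being thrown away. No document gives the prognostic strength of age beyond baseline cognition, diagnosis and comorbidity. At OR 1.3 the variance ratio is about 1.00, and with correlated covariates even OR 2.0 saves only about 4% of variance. This stands and limits the claim.

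**The wording is ambiguous.** A reader might infer that H3/H4 will be adjusted differently from H1. That is not established: the cross-reference could mean the same list or only the same method, and the H1 list may be read as non-exhaustive. But an open list for a primary hypothesis is itself a lack of prespecification.

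**This is a pilot**, and section 10.1 puts feasibility of outcome collection first. That bears on priority. It does not make the cross-reference work.

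**Conclusion.** The point holds as one of prespecification and internal consistency. The H1/H2 list names no demographic variable, H3/H4 point to demographics in H1 that are not there, and the only stated route for age into the primary model is a baseline check. That the check rests on the section 9.5 tests is the natural reading of sections 3 and 9.5 together, though neither says so outright.

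The numerical benefit is secondary and uncertain: from none to about 10% of variance, roughly 0 to 3 points of power, over assumed odds ratios of 1.0 to 2.0 per SD given baseline cognition and site. It shrinks if age correlates with the listed covariates. It applies to the marginal risk difference only if the logistic model is standardised, a step section 9.5 does not describe. The trial is not invalidated. The change is worth making because the loss is negligible even if age is not prognostic.

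**What to change.** In section 9.5:

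1. Add age, as a continuous variable, to the fixed covariate list for H1 and H2, whatever the baseline comparisons show, and make clear that the list is complete.
2. Replace the H3/H4 cross-reference by that same named list.
3. State, here and in section 3, that baseline comparisons are descriptive and do not decide the primary model. Any model adjusted further for observed imbalances would be a sensitivity analysis.
4. State that the marginal risk difference is obtained by standardising the logistic model; otherwise the gain from any covariate does not reach the stated estimand.

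Sex may be added as an option; no calculation here supports or opposes it.

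The cost is a few sentences and one extra parameter. The H1 planning assumptions imply about 56 + 15.7 ≈ 72 declines (112×0.50 + 56×0.28), so one parameter is a small addition; no event rates are given for H2 to H4. No new data are needed. Section 4.3 reports randomisation as complete, so the change should be dated before outcomes are analysed by arm.
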